#### 11.0 SPECIAL INSTRUCTIONS:

N/A

#### 12.0 DATA COLLECTION AND MONITORING

12.1 Data sheets will be kept locked in the Urogynecology Clinic (A3A129) of the clinic tower until transcription into a REDcap database. The data will be subsequently transcribed into REDcap database. Data will be monitored via REDcap.

After transcription into REDCap, the data collection sheets will be kept in a locked cabinet in a locked room (IRD 224) in the IRD building until data analysis is completed, after which they will be destroyed.

Protected Health Information will be kept on the initial contact information sheet, and all additional sheets will be coded. The codes will be kept in a master database on REDCap. Access to identifying information is necessary to link the follow up visit to the initial data collection.

#### 13.0 STATISTICAL CONSIDERATIONS

The sample size of 63 participants per treatment group was calculated to detect a clinically significant mean difference in time to first bowel movement of 12 hours using a two-sample t-test with a standard deviation of 23.7 at 80% power and two-sided significance level of  $p=0.05$ . The sample size was inflated to 70 participants per group to account for an estimated 10% attrition rate.

Summaries of participant characteristics will be described by treatment arm. Participant characteristics will be presented as means and standard deviations for continuous variables and counts and percentages for categorical variables. Comparisons of baseline characteristics will be assessed using two-sample t-tests or the non-parametric corollary for continuous variables and chi-square test for categorical variables. The primary outcome, a comparison of the time to first bowel movement between the treatment and control groups, will be assessed using two-sample t-tests. The secondary outcome, pain at first BM, will also be evaluated using two sample t-tests.

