## 1.0 BACKGROUND AND HYPOTHESES

### 1.1 Background:

Postoperative constipation is among the most common complaints among women after gynecologic surgery. In the early postoperative period a temporary delay in gastrointestinal motility can be expected secondary to manual manipulation of bowel and medications including anesthesia and opiates. Postoperative constipation is a significant problem as return of bowel function is the most common reason for delayed hospital discharge after abdominal surgery. Without intervention, the average time to bowel movement after benign gynecologic and urogynecologic surgery is 4 days +/- 1.5 days. Delayed time to first bowel movement after surgery is often associated with patient discomfort and contributes to a delay in postoperative recovery.

The exact pathophysiology of delayed return of bowel function is unknown. Bayliss and Starling described the presence of inhibitory spinal reflexes acting on the bowel in 1899, which were later identified to be sympathetic inhibitory pathways in the autonomic nervous system. Sympathetic inhibition involves prevention of acetylcholine release from excitatory fibers in the myenteric plexus. The enteric nervous system has also been implicated as Holzer and Lippe suggested the role of Substance P, a neurotransmitter associated with pain. Bult et al. proposed that nitric oxide is the major inhibitory nonadrenergic noncholinergic neurotransmitter in the enteric nervous system. Hormones and neuropeptides such as vasoactive intestinal peptides, inflammation mediated by macrophages and neutrophils, general anesthesia and opioid narcotics may also contribute to the pathophysiology of delayed return to bowel function after surgery.

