## 6.0 STRATIFICATION/DESCRIPTIVE FACTORS/RANDOMIZATION SCHEME

6.1 Stratification factors. N/A

6.2 Descriptive factors. Age, height, weight, self-described race and ethnicity, menopausal status, baseline frequency of bowel movements, laxative use, fiber use, medications used, and baseline stool consistency.

6.3 Randomization plan:

On morning of post-operative day 1, participants who do not meet exclusion criteria will be randomized to the treatment or control group at a 1:1 ratio. Randomization blocks of 6 will be applied in this study to ensure balanced treatment assignments throughout the recruitment period. The randomization assignment list will be generated by the study statisticians. [name]. Ph.D

Participants will be standardly administered 100 g of docusate twice daily for three days per existing routine post-operative care. In addition, we will administer a total of 12 oz of prunes to the study group which are pitted and preservative free. The prunes will be provided to the participant in a sealed package. The study group be instructed to eat 4 oz of prunes daily. The control group will be advised to avoid prune products for 3 days. Each group will be given a diary to note their prune and/or docusate consumption and details of their first bowel movement.

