**If Yes to any of the above, do not enroll.**

# Prunes Data Collection Sheet

## Baseline data collected at time of study enrollment

Participant number # \_\_\_\_\_

Age \_\_\_\_\_ years

Race            White    Black or African American    Asian  
                  American Indian or Alaska Native    Native Hawaiian or Pacific Islander  
                  Other    Multiple races

Hispanic Ethnicity            Yes            No

Parity \_\_\_\_\_

Height            \_\_\_\_\_ cm

Weight            \_\_\_\_\_ kg

Menopausal            Yes            No            Unsure/Not known

Baseline frequency of bowel movements

Multiple times daily            Once a day            Once every other day  
 Twice a week            Once a week

Have you needed to use a laxative at any time in the last 3 months?            Yes            No

Do you take fiber daily or almost daily?            Yes            No

Are you on any of the following medications on a regular basis?            Yes            No

Antimuscarinics (such as Detrol, Ditropan)            Yes            No            No

Iron            Yes            No            No

Calcium channel blocker (such as nifedipine, amlodipine, verapamil, diltiazem)            Yes            No            No

Opioids (such as Percocet, Oxycodone, Tramadol, etc.)            Yes            No            No

Tricyclic antidepressant (such as amitriptyline, imipramine)            Yes            No            No

Bristol Stool Scale (Describe usual stool consistency) \_\_\_\_\_ (Indicate number)

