### If Yes to any of the above, do not randomize.

Was preoperative bowel prep administered?                      Yes                      No

Primary indication for surgery

- Adnexal mass
- Abnormal uterine bleeding (with or without fibroids)
- Fibroid uterus (without abnormal uterine bleeding)
- Pelvic organ prolapse
- Other (Please indicate) \_\_\_\_\_

Procedures performed

- Open abdominal hysterectomy
- Open sacral colpopexy
- Open surgery, other
- Vaginal hysterectomy
- Other vaginal only surgery
- Laparoscopic or robotic hysterectomy (including laparoscopic or robotic assisted vaginal hysterectomy)
- Laparoscopic or robotic sacral colpopexy
- Laparoscopic or robotic surgery, other
- Posterior colporrhaphy
- Burch urethropexy alone
- Other (Please indicate) \_\_\_\_\_

Estimated blood loss \_\_\_\_\_ ml

Surgery start time \_\_\_\_\_

Surgery end time \_\_\_\_\_

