# Prunes Data Collection Sheet

## Self administered survey

Have you had a bowel movement since surgery? Yes No

If Yes, When did you have your first bowel movement?

Date \_\_\_\_\_ Time \_\_\_\_\_

How *painful* was your first bowel movement?

Not at all painful 0    1    2    3    4    5    6    7    8    9    10 Very painful

Which picture best describes your bowel movement (Circle one number)?

1    2    3    4    5    6    7

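### The primary t-test leaves unused two baseline covariates already recorded by randomisation; adjusting for them is a cheap gain in precision

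*Combined protocol and SAP*

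**What the plan says.** Section 13.0 plans for a difference of 12 hours "using a two-sample t-test with a standard deviation of 23.7 at 80% power and two-sided significance level of" 0.05. It arrives at 63 per group, raised to 70 for 10% attrition. The SD carries no unit (hours are implied) and no source. The primary outcome is compared "between the treatment and control groups, will be assessed using two-sample t-tests", with no covariates named. Section 13.0 otherwise uses baseline characteristics only for summaries by arm and for tests of difference between arms.

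Section 6.1 reads "Stratification factors. N/A", and section 6.3 sets 1:1 allocation in blocks of 6 on the morning of postoperative day 1.

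Appendix III records "Baseline frequency of bowel movements" at enrolment, in five ordered categories. Its form for the time of randomisation has a list headed "Procedures performed", which separates open, vaginal and laparoscopic or robotic surgery for most entries.

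Section 1.1 gives the only other spread for this outcome: "the average time to bowel movement after benign gynecologic and urogynecologic surgery is 4 days +/- 1.5 days", in women without intervention.

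**The concern.** How quickly bowel function returns plausibly depends on a woman's usual bowel habit and on how her surgery was done. Both are fixed before allocation, so treatment cannot affect them. With unstratified randomisation the arms can differ on them by chance, and an unadjusted t-test leaves any variation they explain in the error term.

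The stake is precision. The design is sized at the smallest number that reaches 80% power, so any variance the covariates remove widens the cushion without recruiting anyone. Between-arm tests of baseline characteristics, the use section 13.0 does make of these data, do nothing for the precision of the primary estimate.

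**Working it through.** **Inputs from the documents.** Difference 12 h, SD 23.7 (taken as hours), two-sided 0.05, 63 evaluable per arm, 10% attrition (section 13.0); 1:1 allocation (section 6.3).

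**Assumed, because the documents give no figure.** R², the share of outcome variance explained by the two covariates: 0, 10% and 20%. Every first bowel movement time is taken as observed.

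**Step 1: reproduce the plan (two-sample t-test, noncentral t).**
- Standard error = 23.7 × √(2/63) = 4.223 h.
- Noncentrality = 12 / 4.223 = 2.842, with 2 × 63 − 2 = 124 degrees of freedom and critical value 1.979.
- Power = 80.5%. With 62 per arm it is 79.9%, so 63 is the smallest number that reaches 80%.
- 63 / 0.9 = 70. If all 70 per arm are evaluable, power is 84.5%.

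The plan's figures reproduce.

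**Step 2: the adjusted model at 63 per arm.** Bowel frequency as an ordered score takes one term and surgical approach in three levels takes two, making three covariate terms.
- Residual SD = 23.7 × √(1 − R²).
- Degrees of freedom = 2 × 63 − 5 = 121, critical value 1.980.
- Variance inflation for chance imbalance in three terms = (2 × 63 − 3) / (2 × 63 − 6) = 123/120 = 1.025.
- Standard error = residual SD × √(1.025 × 2/63).

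| Assumed R² | Residual SD (h) | Standard error (h) | Noncentrality | Power |
|---|---|---|---|---|
| 0 | 23.70 | 4.275 | 2.807 | 79.5% |
| 10% | 22.48 | 4.056 | 2.959 | 83.5% |
| 20% | 21.20 | 3.824 | 3.138 | 87.6% |

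A simulation with an assumed covariate mix (200,000 trials per row) gave 79.5%, 83.5% and 87.5%.

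**Step 3: break-even.** Adjustment pays once it removes more variance than the imbalance term and the lost degrees of freedom cost. Offsetting the 1.025 alone needs R² = 1 − 1/1.025 = 2.4%. With the degrees of freedom included, adjusted power equals 80.5% at R² = 2.5%.

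**Step 4: effect on the tolerated SD.** The largest outcome SD that keeps 80% power at 63 per arm is 23.85 h unadjusted. Adjusted, it is 23.56 h at R² = 0, 24.83 h at 10% and 26.34 h at 20%.

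**The case against.** The best case for leaving the plan alone has four parts.

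- *The t-test is valid and matches the sample-size calculation.* True. Adjustment is a gain in efficiency and does not repair a bias.
- *R² is unknown and may be small.* Also true. Section 5.2 already excludes bowel disorders, laxative dependence and less-than-weekly bowel movements, which narrows what bowel frequency can explain. But the loss at R² = 0 is about 1 percentage point, and only 2.5% is needed to break even.
- *Surgical approach is not itself a recorded variable.* It has to be derived from a multi-item list, and "Burch urethropexy alone" and the free-text entry carry no route. This stands as a small cost, so the grouping rule must be prespecified.
- *The form asks "Have you had a bowel movement since surgery" and allows No, so some times may not be observed.* This stands as a limit on every power figure here, adjusted or not. If times are missing for this reason, a linear model on hours needs the same rework as the t-test.

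A reader might infer something stronger: that the trial is underpowered because 23.7 is unsourced and power falls below 80% once the SD exceeds 23.85 h, 0.6% above plan. The documents do not support that. Any design that takes the smallest sufficient number has a thin margin. Here it is 6.2% (25.16 h) if all 70 per arm are evaluable, and the true SD could equally be lower: at 22 h, power at 63 per arm is 85.9%.

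A reader might also take the 1.5 days in section 1.1 as a 36 h SD, which would put power at 45.9%. That figure is not labelled an SD and describes women without intervention, whereas both trial arms receive docusate. It does not show 23.7 to be wrong.

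**Conclusion.** The sample size is correct on its inputs, and nothing in the documents contradicts the SD. The point that holds is narrower: two covariates that are plausibly prognostic and recorded before allocation play no part in the primary comparison.

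At SD 23.7 and 63 per arm, using them moves power from 80.5% to 83.5% or 87.6% under an assumed R² of 10% or 20%, and to 79.5% if they explain nothing. The R² values are assumptions, and all outcome times are taken as observed. Adjustment is also no guarantee against a larger SD: with SD 25 h and R² 10%, power is 79.5%.

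This is a cheap improvement. The missing source and unit for 23.7, and its relation to the section 1.1 figure, are a reporting request only.

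**What to change.** Keep 70 per arm and amend section 13.0 as follows.

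1. Primary estimate: the treatment coefficient (difference in mean hours, with 95% CI) from a linear model with treatment, baseline bowel frequency as an ordered score over the five form categories, and surgical approach in three levels.
2. Approach rule for women with several procedures: any open procedure is open; otherwise any laparoscopic or robotic procedure is laparoscopic/robotic; otherwise vaginal only. Entries that name no route are classed from the operative record by someone masked to arm, before outcome data are analysed.
3. Keep the unadjusted two-sample t-test as a sensitivity analysis.
4. As reporting only, state the unit and source of 23.7 and say what the spread in section 1.1 represents.

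The cost is a few sentences in section 13.0, a small amount of masked procedure classing, and about 1 percentage point of power if the covariates have no prognostic value. No extra participants or new form items are needed.

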### 3.6 Evaluation Post-Intervention:

1. All participants will record the date and time of, consistency of and pain associated with their first bowel movement, and answer whether they experienced secondary outcomes as described later.

2. Participants in the treatment arm will also log the number of prunes consumed each day.

2. Participants will be given a stamped and addressed envelope to return the data collection sheets in. Participants will receive a call from an investigator masked to the treatment allocation on postoperative day 3 inquiring about whether the participant has mailed the data collection sheets back. Those who do not answer will be called again the next day.

3. During the phone call, if the participant indicates any postoperative concerns, she will be instructed to contact the on call physician at the LAC+USC Ob/Gyn Triage.

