#### 10.0 CRITERIA FOR EVALUATION AND ENDPOINT DEFINITIONS

The outcome status of all eligible patients will be reported. All eligible patients who begin treatment will be included in the analysis.

Primary endpoints: Time to first bowel movement (in hours)

Secondary endpoints:

1. Stool consistency of the first bowel movement as classified by the Bristol Stool Scale (The stool types are categorical variables, and we will evaluate the differences in the frequencies of the responses by treatment status with a chi-square test)
2. Pain with bowel movement measured (Likert scale, and assessed using t-test or non-parametric methods as appropriate)
3. Satisfaction with bowel regimen (Likert scale, and assessed using t-test or non-parametric methods as appropriate)
4. Satisfaction with surgery overall (Likert scale, and assessed using t-test or non-parametric methods as appropriate)
5. Requirements for laxative (yes or no, assessed as categorical variables and evaluated by chi-square test)
6. Compliance with docusate (percentage of medications consumed, and assessed using t-test or non-parametric methods as appropriate)
7. Compliance with prunes (percentage of prunes consumed, and assessed using t-test or non-parametric methods as appropriate)

8. Adverse events of extreme bloating or flatulence (yes or no, assessed as categorical variables and evaluated by chi-square test)

Compliance with prune consumption will be defined as reported successful consumption of 2/3 of the assigned prunes.

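### No end of observation and no rule for women without a bowel movement, although the only primary analysis is a t-test that needs a time from every woman

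*Combined protocol and SAP*

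**What the plan says.** Section 10.0 defines the primary endpoint as hours to first bowel movement. Section 13.0 states that the comparison "between the treatment and control groups, will be assessed using two-sample t-tests". Non-parametric alternatives are allowed only for secondary endpoints (section 10.0) and baseline variables (section 13.0). On sample size: "The sample size was inflated to 70 participants per group to account for an estimated 10% attrition rate". On the analysis set: "All eligible patients who begin treatment will be included in the analysis".

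The self-administered survey in Appendix III asks "Have you had a bowel movement since surgery? Yes No" and continues "If Yes, When did you have your first bowel movement". After a 'No' it has no field for either an event time or the time at which the answer was given. The Spanish version is the same.

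Section 3.6 says "All participants will record the date and time of, consistency of and pain associated with their first bowel movement". It adds a masked call "on postoperative day 3 inquiring about whether the participant has mailed the data collection sheets back", and "Those who do not answer will be called again the next day". The study calendar in section 9.0 puts that second attempt on postoperative day 5. The prune diary has three day columns and the stool softener diary five. None of these is described as the end of observation, and censoring, imputation or a survival method is mentioned nowhere.

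**The concern.** The survey foresees women with no bowel movement yet, but the analysis does not. A two-sample t-test needs a number from each woman. If it is run on the recorded times, the women left out are those with long times, so the selection is on the primary outcome itself. That also contradicts the plan's own inclusion rule.

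The loss begins on the form. A 'No' with no date cannot later be turned into a censored observation. Because no rule is written, one could also be chosen after the data are seen, in a trial where participants know their allocation and report the endpoint themselves.

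**Working it through.** **1. The plan's own figure.** Standardised difference 12/23.7 = 0.506. The exact two-sample t-test at two-sided 0.05 and 80% power needs 62.2, so 63 per arm. Power at 63 is 80.5%. Inflation: 63/0.9 = 70, where power with complete data is 84.5%. The arithmetic is sound, but it presumes a recorded time from each of the 63.

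**2. Assumptions.** Normal times, SD 23.7 h in both arms (unit taken from the 12 h difference), prune mean 12 h below control. The control mean under docusate is not given, so 60, 72, 84 and 96 h are tried. The last is the four days in section 1.1 (4 × 24 = 96). It is a high end, because that figure is for women without intervention, while here all receive docusate and as-needed laxative is available (section 3.5).

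**3. Common 120 h end, non-events dropped.** The plan states no such end; 120 h is an assumption. Share without an event = 1 − Φ(b), with b = (120 − μ)/23.7. Mean of recorded times = μ − 23.7·φ(b)/Φ(b).

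Example, control mean 96 h:
- Control: b = 1.013, mean = 96 − 23.7 × 0.2389/0.8444 = 89.3 h.
- Prunes (μ = 84): b = 1.519, mean = 84 − 23.7 × 0.1259/0.9356 = 80.8 h.
- Recorded difference 8.5 h in place of 12 h.

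| Control mean (h) | No event, control/prune (%) | Recorded difference (h) | Power, 63 per arm (%) | Power from 70 per arm, no other loss (%) |
|---|---|---|---|---|
| 60 | 0.6/0.1 | 11.7 | 79 | 83 |
| 72 | 2/1 | 11.1 | 77 | 81 |
| 84 | 6/2 | 10.1 | 71 | 76 |
| 96 | 16/6 | 8.5 | 60 | 65 |

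Power is from 20,000 simulated trials per cell.

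**4. No common end, some early mailing.** Suppose a share of the women still waiting at 72 h mail then and the rest wait for the event. Across the four means:
- 10% early: difference 11.7 to 12.3 h, power about 78%.
- 25% early: 11.2 to 12.7 h, 74 to 75%.
- 50% early: 10.2 to 13.5 h, 64 to 68%.

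If everyone waits, nothing is lost.

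**5. Skewed times.** Losses are smaller. At 120 h with non-events dropped, lognormal times give power of 79 to 86% and gamma times 74 to 82%. Lognormal times with 10 to 50% early mailing give 71 to 80%.

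**6. Keeping the women in.** Setting non-events to 120 h leaves t-test power at about 79 to 80% at all four means. The harm comes from dropping them.

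**7. Cost of an open choice (120 h end).** Dropping and ranking last disagree on p < 0.05 in 5, 7, 12 and 22% of trials. With complete data the t-test and rank test already disagree in about 5%. Net of that, the excess is about 0, 1 to 2, 7 and 17 points. With no true effect, taking the best of dropping, setting to 120 h or ranking gives type I error of 6.4 to 8.4%, against about 6% for the best of t-test and rank test on complete data.

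**8. Direction at 120 h.** Take SDs of 18 and 28.3 h, whose average variance is again 23.7²: (324 + 800.9)/2 = 562.4. With the smaller SD in controls the recorded difference is 12.4 to 14.4 h, too large. Reversed, it is 3.2 to 10.8 h, too small.

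**The case against.** The strongest reply is that harm needs two steps the plan does not state: women mail before the event, and they are then dropped. Section 3.6 asks every participant to record her first bowel movement, so many may hold the sheet until then, and section 10.0 argues against dropping anyone. The 120 h end is this review's assumption. The largest losses also need a control mean near the no-intervention figure or heavy early mailing.

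All of that stands as a limit on the size. It does not close the gap. The available text does not tell women to wait, the day 3 call may prompt early return, and keeping everyone in the analysis is an intention without a method. The 10% attrition allowance sizes the trial and does not say how a woman without an event is handled. The consent form and contact sheet (Appendices I and II) are not in the public text, so a return instruction could be there.

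A reader might infer stronger things that the documents do not support:
- That data stop at 72 h, when 31 to 84% of controls would still be waiting under the assumptions used here. Postoperative day 3 is a reminder call and a sheet heading; it is not a stated cut-off.
- That the missing rule alone flips the verdict in 5 to 22% of trials. About 5 points of that is ordinary disagreement between two tests.
- That the trial is underpowered or biased against prunes. Neither follows.

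**Conclusion.** The concern holds as a gap in the plan: no stated end of observation, no time captured after a 'No', and no rule that keeps such a woman in the primary analysis. It should be fixed. Confidence is high on the missing analysis rule and lower on the missing return instruction, given the unseen appendices.

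The size depends on two things the documents do not give: the control mean under docusate and when women mail the sheet. It is nil if all wait, a few points of power at control means of 60 to 72 h with a 120 h end, and about 20 points (80.5 to 60%) at 96 h under normal times. The bias can go either way.

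**What to change.** - Set one last observation time for all women, for example 120 h after the end of surgery, a time the data sheet already collects.
- Tell women to return the sheet after the first bowel movement or at that time, whichever comes first.
- Add to the survey a line for no bowel movement as of a stated date and time.
- Ask bowel-movement status and time in the calls already planned, and reconcile the second-call day between sections 3.6 and 9.0.
- Keep the section 10.0 analysis set and pre-specify one primary analysis: either a rank test with non-events placed last, or a difference in restricted mean time to the fixed end, which stays in hours. Censor women lost earlier at last contact, using the censored-data form of the chosen method (Gehan-Wilcoxon, or a Kaplan-Meier restricted mean).
- State how a bowel movement before randomization on postoperative day 1 is handled.
- Restate power for the chosen method.

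The cost is SAP wording, one survey line, one instruction and one question per call. If all women are observed to 120 h, the rank test has 77 to 79% power with 63 per arm (82 to 83% with 70), about 1 to 4 points below a t-test on complete normal data. The rank test no longer directly tests the 12 h mean difference. The restricted mean has 79 to 81% with equal SDs but 67 to 91% with SDs of 28.3 and 18 h either way round.

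If 10 to 25% of women waiting at 72 h are lost there (equal SDs, control means 72 to 96 h), the figures are 75 to 77% for Gehan-Wilcoxon and 77 to 80% for the restricted mean, against 56 to 73% for the t-test on recorded times. The return instruction therefore matters as much as the choice of test.
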